NCT03984994

Study Protocol and Statistical Analysis Plan

November 22, 2024

Study Design: We will use a randomized, parallel study design, wherein all subjects will undergo all 6 phases of the study and complete each of the research testing visits. After recruitment and screening, all subjects will undergo baseline research testing. Upon completion of baseline testing, subjects will be randomized 1:1, stratified by sex and race, to RT→AEX or AEX→RT. Subjects in the AEX→RT group will then begin 3-month AEX training and the RT→AEX will begin group will begin 3-month RT. Subjects will be in both groups will be tested before and after the RT aspect of the interventions to understand the effects of preceding AEX on responses to RT in terms of muscle morphology and phenotypes. The comparisons in this pilot study involve the changes brought about by RT either with or without preceding AEX.

Interventions:

Aerobic Exercise Training: Participants will exercise for 3 months, 3x/wk on treadmills at an intensity of 60-80% VO₂max for 30-45 min. Participants will continue exercising during research testing. Exercise sessions will be monitored by trained exercise physiologists. Blood pressure and heart rate will be assessed before, during, and after each session. Exercise intensity will be monitored using heart rate monitors. Exercise intensity will be progressed as follows: a) subjects will begin exercising for 30 minutes at 60% of Vo₂max, b) subjects will increase their increase exercise time as tolerated to 45 minutes at 60% of VO₂max, c) subjects will increase their exercise intensity to 70% VO₂max and 80% VO₂max, respectively, as tolerated. Subjects will be encouraged to maintain their body weight and food may be given to supplement subjects' diets if weight loss is excessive at more than 2% per month.

Strength Training: Participants will participate in strength training for 3 months, 3x/wk. This will consist of approximately 2-3 sets of approximately 8-15 repetitions for each exercise as tolerated. Training may be performed on Keiser K-300 air powered machines utilizing pneumatic resistance (Leg Extension Machine, Leg Curl Machine, Leg Press Machine) or comparable strength training machines. Each session of ST will take approximately 30 minutes. Exercise sessions will be monitored by trained exercise physiologists. Blood pressure and heart rate will be assessed before and after each session.

Research Tests - Before and after the interventions, the following tests will take place:

Body Composition: Total and regional fat mass, lean tissue mass, % body fat, bone mineral content, and bone density will be determined by dual-energy x-ray absorptiometry (DXA). Body circumference at several sites of the body will be taken with a measuring tape. Computed tomography scans of the abdomen and thigh and lower leg are done to quantify regional fat and muscle distribution.

Strength Testing: Subjects will perform 3 sets of knee extension Isometric Maximal Voluntary Contractions (IMVCs) on an isokinetic device (BIODEX System) with 1-2 mins of resting periods between sets. Knee extension will be performed in a seated position with the testing leg positioned at 60 degrees of knee flexion. For every trial subjects will properly stabilized to ensure minimal movement artifacts. Additionally, verbal encouragement, as well as visual feedback from the torque recordings will be provided during task to potentiate the volitional maximal contraction.

Muscle Biopsy: Participants will be asked to fast overnight (~8-12 hours) prior to the biopsy. A biopsy (approximately 300-1000mg) will be obtained from the vastus lateralis muscle after local anesthesia with 0.5-1% lidocaine. A scalpel is used to make a 1/4" incision and a Bergstrom cutting trocar and outer needle are inserted into the vastus lateralis muscle.

Statistical Analysis: Data will be verified by the PI and exploratory analyses will determine the distribution characteristics of the data. The general statistical methods for Aims 1 and 2 will be the same and our analyses will include data only on the effects of RT (i.e., the change brought about by RT in each arm/group), consistent with the aims of the study. Primary and secondary outcomes are evaluated before and after 3-month RT in each arm of the study (i.e., baseline to 3-month change in the RT→AEX arm, and 3-month to 6-month change in the AEX→RT arm). The analysis plan involved ANCOVA or repeated measures ANCOVA to assess the effects of the interventions; however, there was insufficient power for planned analyses and t-tests with a P-value of P ≤ 0.05 were used to compare the changes brought about by RT in the two arms/groups.

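### Does treadmill training that continues through the AEX→RT arm's pre-RT tests call for a change to the analysis?

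*Combined protocol and SAP*

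**What the plan says.** Under Interventions, the Aerobic Exercise Training paragraph states "Participants will continue exercising during research testing". The training itself is "Participants will exercise for 3 months, 3x/wk on treadmills at an intensity of 60-80% VO₂max for 30-45 min". The Strength Training paragraph has no matching sentence.

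Study Design places the entry tests before allocation: "all subjects will undergo baseline research testing", then "Upon completion of baseline testing, subjects will be randomized 1:1".

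Statistical Analysis fixes the windows as "baseline to 3-month change in the RT→AEX arm, and 3-month to 6-month change in the AEX→RT arm" and limits the data: "our analyses will include data only on the effects of RT". It adds that ANCOVA or repeated measures ANCOVA was planned, and that t-tests on the RT changes replaced it for lack of power.

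Under Research Tests, the only preparation given for the biopsy is "Participants will be asked to fast overnight (~8-12 hours) prior to the biopsy". Strength testing gives rest between sets but no interval since the last training session.

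**The concern.** The pre-RT value is subtracted in each arm's change score. In RT→AEX it comes from people who have done no study training. In AEX→RT it comes from people still on the treadmill three times a week, possibly tested soon after a session. Both tests use the thigh (vastus lateralis biopsy, knee extension), so a temporary effect of recent exercise on the AEX→RT starting value is conceivable.

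Such an effect would appear as a difference in RT response although RT acted equally in both arms. The AEX→RT entry values, which could show how far that arm moved before RT began, are left out of the comparison. A reader of the t-test alone could not tell a changed response to RT from a displaced starting value.

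**Working it through.** **Which visits are affected**

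| Arm | Pre-RT visit | Post-RT visit |
|---|---|---|
| RT→AEX | Baseline, before any study training | Month 3, after RT |
| AEX→RT | Month 3, treadmill training continuing | Month 6, after RT |

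RT→AEX does its AEX after its analysed window. Both post-RT visits follow RT, so they do not create this imbalance. The instruction therefore reaches one cell of the four.

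**Effect on the comparison**

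Let Y0, Y3 and Y6 be the entry, month-3 and month-6 means.

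- RT-change contrast: D_RT = (Y6 - Y3) in AEX→RT minus (Y3 - Y0) in RT→AEX.
- If the AEX→RT Y3 moves by s and Y6 does not, D_RT moves by -s.
- Entry-anchored contrast: D_entry = (Y6 - Y0) in AEX→RT minus (Y3 - Y0) in RT→AEX. It does not contain the AEX→RT Y3.
- D_entry - D_RT = (Y3 - Y0) in AEX→RT.

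**Size, on assumed inputs**

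The documents give no sample size, SD or effect size, so there is no figure of theirs to reproduce. Assumed here: 8, 12 or 20 per arm; sessions on three weekdays with weekday-morning tests, so that 2 of 5 slots (40%) fall near a session; and an acute shift of 0.25 to 0.5 SD of the change score. The mean shift is then 0.40 × 0.25 = 0.10 to 0.40 × 0.50 = 0.20 SD. Two-sided 5% rejection with no true difference comes from the noncentral t with df = 2n - 2 and noncentrality s√(n/2):

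| n per arm | s = 0.10 | s = 0.20 | s = 0.25 | s = 0.50 |
|---|---|---|---|---|
| 8 | 5.4% | 6.6% | 7.5% | 15.4% |
| 12 | 5.6% | 7.6% | 9.0% | 21.6% |
| 20 | 6.1% | 9.5% | 12.0% | 33.8% |

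The last two columns require every AEX→RT participant to be affected, for which the documents give no support.

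**Would the entry-anchored contrast settle the matter?**

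Take an RT gain of 0.5 in both arms, a lasting AEX gain of +0.3 that persists to month 6, an acute dip of -0.3 at month 3, and an entry mean of 0.

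- AEX→RT: Y3 = 0 + 0.3 - 0.3 = 0, and Y6 = 0.3 + 0.5 = 0.8.
- D_RT = (0.8 - 0) - 0.5 = 0.30.
- D_entry = (0.8 - 0) - 0.5 = 0.30.
- Without the dip, Y3 = 0.3 and D_RT = (0.8 - 0.3) - 0.5 = 0.

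The two contrasts agree exactly, yet the dip produces the whole RT-change difference. Disagreement is no clearer: the gap is the total AEX→RT change from entry to month 3, which may be acute, lasting or both.

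**Precision of the gap**

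The within-arm 95% half-width is t(0.975, n - 1)/√n, in SD of the change: 0.84 at n = 8, 0.64 at n = 12 and 0.47 at n = 20. The shift to be detected is 0.10 to 0.20.

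**The case for a change.** The strongest case for acting is that the asymmetry is built into the visit structure, the -s identity needs no assumption about sample size, and the remedy looks almost free. Entry tests are planned for everyone and sessions are supervised, so the session-to-test interval and three AEX→RT means might be reported without a new visit. Nor would the ANCOVA that was dropped have helped, since the pre-RT value it would adjust for is measured after randomization in one arm only.

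The structural point and the identity stand. The case for a change does not, for four reasons.

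- The comparison is of RT after AEX with RT alone. A lasting AEX effect on the month-3 value belongs to that question; only a purely temporary component would be a bias, and its presence, size and direction are unknown.
- Entry values are not the only reference for the month-3 value. Because allocation follows baseline testing, the arms have equal expected entry values, so the RT→AEX baseline mean, already in the analysis, serves in expectation. The AEX→RT entry values would add precision, but no separation of acute from lasting effects.
- Reporting the interval from last session to test would inform a reader, provided the times were recorded; the protocol says sessions are monitored, not that dates and times are kept. It would not alter the t-test.
- A required exercise-free interval could apply only to future visits. Statistical Analysis describes the t-tests in the past tense, so testing is probably complete.

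**Conclusion.** No change to the plan is needed. The AEX→RT pre-RT tests do take place under a different exercise condition from the RT→AEX pre-RT tests, and a temporary effect of s there would move the result by -s. The likely cost is small: 0.10 to 0.20 SD and a rejection rate of 5.4% to 9.5% in place of 5%, if 40% of tests fall near a session, the acute shift is 0.25 to 0.5 SD and there are 8 to 20 per arm. All of these inputs are assumed.

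The additional analysis that suggests itself cannot identify an acute effect whether the contrasts agree or differ, and it is too imprecise for a shift of that size. The unstated interval is a missing detail that authors can supply when reporting, where records allow, with a sentence noting that acute and lasting AEX effects cannot be separated at that visit. Neither step alters the comparison, the test or its result.

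### Does dropout during aerobic training undermine the comparison of resistance-training changes, given that no analysis set is named?

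*Combined protocol and SAP*

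**What the plan says.** The Study Design section places randomisation before any training: "Upon completion of baseline testing, subjects will be randomized 1:1, stratified by sex and race, to RT→AEX or AEX→RT". One arm goes straight to RT. For the other, "Subjects in the AEX→RT group will then begin 3-month AEX training", with RT afterwards. On completion it says only that "all subjects will undergo all 6 phases of the study and complete each of the research testing visits".

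The Statistical Analysis section sets the outcome windows as the "baseline to 3-month change in the RT→AEX arm, and 3-month to 6-month change in the AEX→RT arm". It then reports that "there was insufficient power for planned analyses" and that "t-tests with a P-value of P ≤ 0.05 were used to compare the changes brought about by RT in the two arms/groups".

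Neither section names an analysis set, gives a rule for people without follow-up, or asks for losses by phase and arm. No sample size, SD or dropout rate is given.

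**The concern.** The two arms need different visits to yield an RT change: months 0 and 3 in RT→AEX, months 3 and 6 in AEX→RT. Three months of AEX lie between randomisation and the start of the second window. Someone who leaves during AEX and is not tested again drops out of a t-test on changes if allocated to AEX→RT. The same person allocated to RT→AEX has already supplied the needed change. That is exclusion after randomisation in one arm only, in the contrast the trial exists to make.

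If people who leave during AEX would also have responded less to RT, the remaining AEX→RT group is a favourable selection, and part of the apparent benefit of prior AEX is a difference between stayers and leavers. If leavers would have responded better, the bias runs the other way. The remark about insufficient power invites the thought that people were lost, though it fits low enrolment equally well.

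**Working it through.** The documents state no figure to reproduce. The windows, the timing of randomisation, the 1:1 ratio and the 0.05 threshold come from the documents. Every loss rate, correlation and arm size below is an assumption. The t-test is taken as two-sided, which the documents do not state.

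**1. Share with an RT change.** With loss q per 3-month phase, the share missing is L_R = q in RT→AEX and L_A = 1 − (1 − q)² in AEX→RT.

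| q | L_R | L_A | gap |
|---|---|---|---|
| 0.10 | 0.10 | 0.19 | 0.09 |
| 0.20 | 0.20 | 0.36 | 0.16 |
| 0.30 | 0.30 | 0.51 | 0.21 |

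**2. Bias identity.** The mean over all randomised is (1 − L) × stayers + L × leavers, so stayers minus all = L × d, where d is the stayer-minus-leaver difference in mean RT change, in SD. The bias of the contrast is L_A × d_A − L_R × d_R. With equal d and q = 0.20 this is 0.16 × d: 0.04, 0.08 and 0.12 SD for d = 0.25, 0.5 and 0.75.

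**3. Trait scenarios at q = 0.20.** A normal dropout trait has correlation c with RT change, and those lowest on it leave. Let m(p) = φ(z_p)/(1 − p), so m(0.20) = 0.350 and m(0.36) = 0.585.

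| Scenario | Formula | c = 0.3 | c = 0.5 |
|---|---|---|---|
| A: trait alone decides AEX loss; RT loss unrelated | c × m(0.20) | 0.105 | 0.175 |
| B: trait explains half of AEX loss; RT loss unrelated | 0.71 × c × m(0.20) | 0.074 | 0.124 |
| C: trait alone decides loss in both phases | c × [m(0.36) − m(0.20)] | 0.070 | 0.117 |
| D: trait explains half of loss in both phases | simulation | 0.060 | 0.100 |

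D removes 20% of those still present in each phase, which keeps L_A at 36%. Applying one fixed dropout threshold twice gives 0.045 and 0.073, but total loss is then only about 31%, so those values are not comparable with A to C.

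Scenario A scales with loss: 0.058 and 0.097 SD at q = 0.10; 0.149 and 0.248 SD at q = 0.30.

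**4. Effect on the error rate.** Noncentral t with noncentrality bias/SE and SE = √(1/n_R + 1/n_A), in SD:

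- 20 per arm: 20 × 0.80 = 16 and 20 × 0.64 = 12.8 analysed, SE = 0.375. Error is about 5.3% to 7.3% over A to D.
- 10 per arm: 8 and 6.4 analysed, SE = 0.530. Error is about 5.1% to 6.1%.

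**5. How far leavers would have to differ.** Suppose loss occurs only during AEX and the result favours AEX→RT. The value of d that moves P to 0.05 is (t_obs − t_crit) × SE / L, holding the SE fixed. For 20 versus 16 analysed and P = 0.03: (2.265 − 2.032) × 0.335 / 0.20 = 0.39 SD.

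| Analysed | SE | L | d if P = 0.03 | d if P = 0.01 |
|---|---|---|---|---|
| 20 v 16 | 0.335 | 0.20 | 0.39 | 1.17 |
| 20 v 19 | 0.320 | 0.05 | 1.48 | 4.42 |
| 10 v 8 | 0.474 | 0.20 | 0.62 | 1.90 |

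**The case for a change.** The best case for acting is that the asymmetry follows directly from the stated windows, and that the same P-value is fragile or sturdy depending on a count the plan does not ask for. At 20 per arm, P = 0.03 gives way at 0.39 SD with four people lost, but needs 1.48 SD with one. The completion statement in the Study Design section is an expectation, not an analysis set, and the restriction to RT effects says which data are used, not which people. A loss table costs almost nothing.

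All of that stands as a case for reporting. Four things limit it as a case against the plan:

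- Keeping the RT→AEX participant lost during later AEX is an inference. The text is equally compatible with analysing only 6-month completers, in which case AEX loss removes people from both arms.
- Loss must mean absence from month-3 or month-6 testing. Someone who stops AEX training but is tested and does RT still contributes.
- No loss is shown.
- The available additions do not cure the bias. All randomised participants with values before and after RT is the set a t-test on changes uses anyway, and it is the set that produces the asymmetry. Comparing month-0 characteristics of one to four leavers says very little. A mixed model on everyone randomised can reduce, leave or increase the bias, depending on how the month-0 outcome relates to dropout and to RT change.

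**Conclusion.** The observation is correct but calls for no change. The RT-only contrast is what the study set out to estimate, and placing AEX before RT in one arm unavoidably puts that arm's window later. No stated rule is shown to give a wrong result, and no better primary method is on offer. The missing analysis set is a gap that analysts fill sensibly by using whoever has both values, or completers.

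If losses occurred and were related to RT response, the bias would be about 0.06 to 0.17 SD at 20% loss per phase and correlation 0.3 to 0.5. It would be smaller at lower loss and larger at 30%. At 10 per arm and 20% loss that compares with a standard error of 0.53 SD, so imprecision dominates in what the protocol calls a pilot. With full retention, or loss unrelated to response, the bias is zero. These sizes rest wholly on assumed loss rates, correlations and arm sizes.

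Stating the set and giving losses by phase and arm belongs in the report of results. The Statistical Analysis section describes the t-tests in the past tense, so anything added now would be post hoc description.

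### Low power is the stated reason for replacing ANCOVA with unadjusted t-tests, but dropping adjustment adds no information and loses power if the sex and race strata predict the RT change

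*Combined protocol and SAP*

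**What the plan says.** The Study Design section of the combined protocol and SAP states that "subjects will be randomized 1:1, stratified by sex and race". It describes the work as a pilot: "The comparisons in this pilot study involve the changes brought about by RT either with or without preceding AEX".

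The Statistical Analysis section defines the compared quantity as the change over the RT period, namely "baseline to 3-month change in the RT→AEX arm, and 3-month to 6-month change in the AEX→RT arm". On the method it says "The analysis plan involved ANCOVA or repeated measures ANCOVA to assess the effects of the interventions". It then continues: "however, there was insufficient power for planned analyses and t-tests with a P-value of P ≤ 0.05 were used to compare the changes" that RT produced in the two arms.

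The document gives no sample size, power figure, target difference, SD, pre-to-post correlation or list of ANCOVA covariates. It attaches no significance level to the ANCOVA, and it states no interval or adjusted estimate for the replacement analysis. The past tense suggests that the t-tests may already have been run.

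**The concern.** Power depends on the number of participants, the true effect, the residual variance and the significance level. Moving from a covariate model to a t-test changes neither the participants nor the effect. It does return the degrees of freedom that the covariates used, but it puts back into the error term any variance the covariates explained. Sex and race were thought important enough to stratify on, and the t-test then discards them. If they predict the response to RT, the test is weaker than the adjusted comparison in a study already described as short of power.

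What is at stake is how usable the pilot's result is. The question is how much preceding AEX changes the RT response. With low power, a bare cutoff says little about which differences remain plausible. An estimate with its interval says this directly, and adjusting for prognostic strata narrows the interval.

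**Working it through.** **Inputs from the document.** 1:1 allocation stratified by sex and race; outcome is RT change in each arm; t-test judged at P ≤ 0.05. The plan has no power figure to reproduce.

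**Assumptions.** Two-sided 5%; sex and race each at two levels; n = 5, 10 or 20 per arm; true difference D in SDs of RT change; R² is the share of variance in RT change explained by sex and race (0 or 0.20).

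**Formulas, with strata balanced across arms.**
- t-test: 2n − 2 df; 95% CI half-width t(0.975, 2n − 2) × √(2/n).
- Model of RT change on arm, sex and race: 2n − 4 df; half-width t(0.975, 2n − 4) × √(2(1 − R²)/n); noncentrality D√(n/2)/√(1 − R²).

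**Strata prognostic (R² = 0.20, D = 0.5).** At 10 per arm the adjusted noncentrality is 0.5 × √5/√0.8 = 1.118/0.894 = 1.25. At 20 per arm it is 0.5 × √10/√0.8 = 1.581/0.894 = 1.77. Simulation with stratified allocation gave adjusted power of 21.5% and 40.3%. The unadjusted figure varies with how the strata are set up and balanced in the simulation, so it is shown as a range. When allocation balances the strata, the t-test's standard error still contains the between-stratum variance, so the test is conservative. At 10 per arm the half-width is 2.101 × √0.20 = 0.940 SD unadjusted and 2.120 × √0.16 = 0.848 SD adjusted.

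**Strata not prognostic (R² = 0).** The adjusted model only loses 2 df.

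| n per arm | R² | D (SD) | Power, t-test | Power, adjusted |
|---|---|---|---|---|
| 10 | 0.20 | 0.5 | 16–20% | 21% |
| 20 | 0.20 | 0.5 | 31–36% | 40% |
| 10 | 0 | 0.5 | 18.5% | 18.3% |
| 10 | 0 | 1.2 | 71.8% | 71.2% |
| 20 | 0 | 0.5 | 33.8% | 33.7% |
| 5 | 0 | 1.2 | 38.6% | 35.9% |

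At 5 per arm the cost of adjusting is 38.6 − 35.9 = 2.7 points at D = 1.2 and 4.2 points at D = 1.8, if strata are perfectly balanced. Four strata cannot be expected to balance exactly at that size. Simulations with residual imbalance put the cost at about 5 to 6 points, with about 7 in one run at D = 1.8. The half-width rises from 2.306 × √0.40 = 1.46 SD to 2.447 × √0.40 = 1.55 SD with perfect balance, and to about 1.60 SD with imbalance. At 10 per arm it goes from 0.940 to 0.948 SD.

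**If the planned model was repeated measures without covariates.** With two arms and two time points, the arm-by-time test is the t-test on change. A simulated data set with 12 per arm gave t² = F = 0.16904 on 22 df, P = 0.6849 for both. In that case the switch changes nothing.

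**If the planned ANCOVA included the pre-RT value.** With pre-to-post correlation r, the variance of the arm difference under ANCOVA relative to the change score is (1 + r)/2: 0.75, 0.85 and 0.95 at r = 0.5, 0.7 and 0.9. For a difference of 0.8 SD at a single time point, 20 per arm and r = 0.5 give 69% power for the t-test and 80% for ANCOVA. At 5 per arm and r = 0.9 the order reverses: 70% for the t-test against 64% with one covariate, or 43% with three if the extra two are uninformative. Without r, n or the covariates, the direction cannot be settled.

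**The case against.** The strongest reply is that the sentence may mean only that there were too few participants to support covariate models, so a simpler test was used. This has force. At 5 per arm, adjusting for uninformative strata costs several points of power, and an ANCOVA with several weak covariates can cost far more. The simplification may have been sensible if the arms were that small. Nothing in the document says whether they were, and at 10 or more per arm the argument largely disappears.

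Several stronger readings are tempting, and the document does not support them:
- A reader might infer that the plan presents the t-test as restoring power. It gives low power as the reason for the switch but never claims that.
- A reader might infer that a t-test can regain only the covariates' degrees of freedom. That fails for an ANCOVA including the pre-RT value, where residual variance changes too.
- A reader might infer that P ≤ 0.05 was carried over from the ANCOVA. The criterion is attached to the t-tests only.
- A reader might infer that no interval will be reported, or that P > 0.05 will be taken as no effect. The text is silent on both. A two-sample t-test yields an interval directly, so its absence from so short a plan is missing detail and not in itself an error. The same applies to primary and secondary outcomes not being assigned to tiers.

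It is also fair to say that every magnitude above is conditional on assumed inputs and none measures this trial.

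**Conclusion.** The point stands in a limited form. Insufficient power does not justify moving to an unadjusted comparison that ignores the randomisation strata. If sex and race explain 20% of the variance in RT change, the t-test gives up about 1 to 5 points of power at 10 per arm (21 − 20 to 21 − 16) and 4 to 9 points at 20 per arm (40 − 36 to 40 − 31), for a true difference of 0.5 SD. If they explain nothing, adjustment is nearly free at 10 or more per arm with balanced strata and costs about 3 to 6 points at 5 per arm. These figures rest on assumed numbers per arm, two-level strata and an assumed R². The effect of the switch relative to an ANCOVA that included the pre-RT value cannot be determined from the document. The point concerns efficiency and usable reporting; it is not a claim that the t-tests are biased or that their type I error is inflated. It is worth considering, with medium confidence.

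**What to change.** For each outcome, make the main result the between-arm difference in RT change with its 95% CI, from a linear model of RT change on arm, sex and race. Both covariates are fixed before randomisation. The pre-RT value is not, because in the AEX→RT arm it is measured at 3 months, after AEX. Show the t-test difference and its 95% CI beside it, labelled as a sensitivity analysis, so that the two are ranked. State the number analysed per arm, and do not read P > 0.05 as showing no effect of preceding AEX. If the arms are so small that strata are empty or nearly so, say so and rely on the unadjusted interval.

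The cost is one extra model per outcome on data already collected, and it can be done even if the t-tests are finished. The interval is wider if sex and race predict nothing: about 1.46 to 1.60 SD at 5 per arm, and 0.94 to 0.95 SD at 10. The adjusted model would be added after the switch, so the report should say so and explain that its covariates come from the randomisation scheme.
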